1. LIST OF ABBREVIATIONS

Abbreviation	Definition
AEM	Adverse Event Monitoring
IEC	Independent Ethics Committee
IRB	Institutional Review Board
MFDS	Ministry of Food and Drug Safety
NIS	Non-Interventional Study
PMS	Post-Marketing Surveillance
SAP	Statistical Analysis Plan
SRSD	Single Reference Safety Document

3. AMENDMENTS AND UPDATES

Amendment number	Date	Substantial or administrative amendment	Protocol section(s) changed	Summary of amendment(s)	Reason
1	February 23, 2015	Administrative amendment	Refer to the Summary of Changes	Refer to the Summary of Changes	Amended according to the supplementation request by MFDS
2	April 16, 2015	Administrative amendment	Refer to the Summary of Changes	Refer to the Summary of Changes	Rewording appropriate for the retrospective study method
3	September 24, 2015	Administrative amendment	Refer to the Summary of Changes	Refer to the Summary of Changes	Reply to MFDS inquiries and rewording
4	16 October 2017	Substantial amendment	Refer to the Summary of Changes	Refer to the Summary of Changes	Rewording to adjust the number of target patients
5	17 May 2018	Administrative amendment	Refer to the Summary of Changes	Refer to the Summary of Changes	Amended according to the supplementation request by MFDS

4. MILESTONES

Milestones	Planned Dates
Start date of data collection	02 January 2016
End date of data collection	30 September 2017
First year (1-1) periodic report (MFDS)	30 November 2014
First year (1-2) periodic report (MFDS)	30 May 2015
Second year (2-1) periodic report (MFDS)	30 November 2015
Second year (2-2) periodic report (MFDS)	30 May 2016
Third year annual report (MFDS)	30 November 2017
Re-examination report (MFDS)	29 June 2018

Abbreviation: MFDS = Ministry of Food and Drug Safety

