5. RATIONALE AND BACKGROUND

Xyntha Solofuse prefilled syringe was approved on March 31, 2014 in Korea. The Xyntha Solofuse prefilled syringe is administered by intravenous infusion after reconstitution of the freeze-dried powder with the diluent (0.9% Sodium Chloride). This drug consists of the identical ingredients with the previous Xyntha injection, and the drug and the diluent are supplied within the prefilled dual-chamber syringe. As required for all new drugs approved by the Ministry of Food and Drug Safety (MFDS), information on the safety and efficacy of the new drug should be provided based on the study conducted with at least 600 study subjects who are administered this drug in the setting of routine practice for 4 years from the approval date (March 31, 2014 - March 30, 2018). This non-interventional post-marketing surveillance (PMS) study is an obligation to the MFDS. However, it is expected that about 95 subjects who received this drug should be recruited and registered as study subjects. Considering the number of subjects who meet the analysis exclusion criteria, safety and efficacy information for at least 86 subjects will be collected for all subjects who received this drug during the study period. Background information on Xyntha Solofuse prefilled syringe can be obtained from the current version of the local product document, which is the single reference safety document (SRSD) for information relating to the Xyntha Solofuse prefilled syringe in this study.

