7.2.3. Study Period

As specified in the product approval issued by the Ministry of Food and Drug Safety, the study will be conducted for 4 years from the approval date of March 31, 2014 to March 30, 2018.

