7.5. Study Size

The calculation of sample size is not applicable for this study. At least 600 study subjects will be enrolled in this study to meet the MFDS requirements. In this study, 14 sites conduct complete enumeration study data collection for more than 86 subjects who administered this drug during study period .

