6.7. Efficacy Analyses

A descriptive summary will be performed for efficacy endpoint.

- 1) On-demand treatment (surgery)
 - ① The best responses to all the injection of the Xyntha Solofuse prefilled syringe used to treat bleeding (4 point scale: excellent, good, moderate, and no response) will be presented in frequency and percentage.
 - ② Number of observations of less than expected therapeutic effect (LETE) will be presented by n, mean, SD, median, minimum and maximum or frequency and percentage.
 - ③ Mean infusion dosage will be presented by n, mean, SD, median, minimum and maximum.
- 2) On-demand treatment (bleeding)
 - ① The best responses to all the injection of the Xyntha Solofuse prefilled syringe used to treat bleeding (4 point scale: excellent, good, moderate, and no response) will be presented in frequency and percentage.
 - ② Number of observations of less than expected therapeutic effect (LETE) will be presented by n, mean, SD, median, minimum and maximum or frequency and percentage.
 - ③ The number of infusions of Xyntha Solofuse prefilled syringes used to treat each new bleeding episode is descriptive statistics of medication treatment duration will be presented in n, mean, SD, median, minimum and maximum or frequency and

Statistical Analysis Plan for rPMS

percentage.

- ④ Mean infusion dosage will be presented by n, mean, SD, median, minimum and maximum.

3) Prophylactic Therapy

- ① Subjects who have experienced bleeding (overall, spontaneous) will be presented in frequency and percentage.

- ② Annualized Bleeding Rates (ABRs)

The annualized bleeding rate is the incidence rate of bleeding per year. Since the follow up period for each patient is 6 months (= 0.5 year), the ABR is calculated as follows.

N=Number of patients who received prophylactic treatment.

X=Number of patients who have bleeding among the patients included in the patients who received prophylactic treatment

$$ABRs = \frac{X}{N \times 0.5}$$

- ③ Number of observations of less than expected therapeutic effect (LETE) will be presented by n, mean, SD, median, minimum and maximum or frequency and percent.
- ④ Mean infusion dosage will be presented by descriptive statistics as n, mean, SD, median, minimum and maximum.
- ⑤ Total factor consumption (total infusion dosage) will be presented by descriptive statistics as n, mean, SD, median, minimum and maximum.

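### Planned data collection stops on 30 September 2017, but the protocol promises data on all users in a study period running to 30 March 2018; the cut-off dates need reconciling and the ABR should use observed time.

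*Protocol*

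**What the plan says.** Protocol section 4 (Milestones) lists planned dates. The "Start date of data collection" is 2 January 2016, the "End date of data collection" is 30 September 2017, and the re-examination report is due on 29 June 2018.

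Protocol 7.2.3 says that "the study will be conducted for 4 years from the approval date of March 31, 2014 to March 30, 2018". The SAP's opening background text repeats the same four years and gives no data cut-off.

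Two places describe coverage. Protocol section 5 says that "safety and efficacy information for at least 86 subjects will be collected for all subjects who received this drug during the study period", having first said that "it is expected that about 95 subjects who received this drug should be recruited and registered as study subjects". Protocol 7.5 says that "14 sites conduct complete enumeration study data collection for more than 86 subjects who administered this drug during study period". Protocol section 10 adds that the final report will contain everything collected over the whole study period.

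On follow-up, Protocol 7.1 and SAP 2.2 allow up to six months from first administration. Their only rule for a shorter window concerns subjects who do not complete six months of treatment. SAP 6.7 nevertheless sets the ABR denominator at N × 0.5, on the ground given there: "Since the follow up period for each patient is 6 months (= 0.5 year".

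**The concern.** The date on which collection stops and the period over which all users are promised do not match, and nothing in the text bridges them. A user first infused after 30 September 2017 falls inside the promised population but cannot be in the data. A user first infused in the six months before that date can be in the data, but only with a shortened window. Neither document says how a window cut by the calendar, as opposed to one ended by stopping treatment, is to be analysed.

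Two things are at stake. First, a final report that repeats the complete-enumeration statement for the four-year period would claim more coverage than the milestone allows. Second, a truncated subject has less time to bleed or to have an adverse event recorded. The ABR formula still counts that subject as half a year, so the rate is pulled down. Adverse event results are reported as proportions of subjects (SAP 6.6), so they move the same way. That includes any factor VIII inhibitor finding, which is the primary objective.

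**Working it through.** **The plan's own figure.** From 31 March 2014 to 30 March 2018, counting both ends, is 1,461 days, or 1,461 / 365.25 = 4.00 years. The stated four-year study period reproduces.

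**Start dates that cannot be collected** (milestone taken literally). From 1 October 2017 to 30 March 2018: 31 + 30 + 31 + 31 + 28 + 30 = 181 days. 181 / 1,461 = 12.4%.

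**Start dates that cannot give six months.** Six months ending on 30 September 2017 begin on about 30 March 2017. From 31 March to 30 September 2017: 1 + 30 + 31 + 30 + 31 + 31 + 30 = 184 days. 184 / 1,461 = 12.6%.

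**Together.** 181 + 184 = 365 days. 365 / 1,461 = 25.0% of possible start dates.

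**Number of subjects.** The documents give no distribution of start dates, so any count rests on an assumption. With even uptake over the four years, the result depends on what the 95 (or the analysable 86) stands for:

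- If it counts all users in the study period: missed = 95 × 181 / 1,461 = 11.8 and truncated = 95 × 184 / 1,461 = 12.0. For 86, the figures are 10.7 and 10.8.
- If it counts only users who started by 30 September 2017 (1,461 − 181 = 1,280 days): further users missed = 95 × 1,461 / 1,280 − 95 = 13.4 and truncated = 95 × 184 / 1,280 = 13.7. For 86, the figures are 12.2 and 12.4.
- If nobody started after March 2017, both numbers are zero.

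**Effect on the ABR denominator** (even uptake again, and prophylaxis subjects spread like the rest). Truncated subjects are 184 / 1,280 = 14.4% of those included, and on average have about half of the six months. Available time is then 1 − 0.144 × 0.5 = 0.928 of what N × 0.5 assumes, so the denominator is too large by a factor of 1 / 0.928 = 1.08, about 8%. This is an illustration, and it too starts at zero.

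**Other readings of the milestone row.** 30 September 2017 plus six months is 30 March 2018, the last day of the study period. If the row means the last permitted first dose, the 184-day truncation disappears but the 181 days of missed starters remain. If collection in fact ran past the milestone, the row itself is wrong.

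**Would moving the end date be enough?** With collection to 30 March 2018, no start date in the period is missed, but the last 181 days of starters still have less than six months. Six months for everyone would need records to about 30 September 2018, after the report due on 29 June 2018.

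**The case against.** The strongest reply is that this is a mismatch of planned dates in a descriptive, uncontrolled study. Protocol 7.5 names no calendar date. The end of 30 March 2018 comes from reading it with 7.2.3, which says when the study is conducted. The milestones are headed as planned dates, so one row may simply be out of date. All of this is fair, and it limits what can be concluded. It does not remove the conflict: the amendment log has entries dated 16 October 2017 and 17 May 2018, both after the milestone, and the current text still carries both dates with nothing between them.

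Several stronger readings are tempting and are not supported:

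- A reader might infer that about a dozen users were in fact lost and another dozen cut short. The documents cannot show this. The dates are planned, the even uptake is assumed, and the true number could be zero.
- A reader might take the missed users to be part of the 95. Section 5 describes the 95 as subjects expected to be registered, so missed users may be additional. The October 2017 amendment, which adjusted the target number after the milestone had passed, fits that reading without proving it.
- A reader might say that the SAP assumes six months for everyone. Only the ABR formula does. SAP 2.2 and 4.6 provide for subjects who do not complete six months of treatment, so a short window does not in itself breach the plan.
- A reader might infer that enumeration is the plan's argument for representativeness. The plan makes no such argument; Protocol 7.9 claims only observation under actual conditions of use.
- A reader might infer from the January 2016 start that earlier users are excluded too. Collection is retrospective, so that date does not limit first administration.

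The ABR formula would be wrong for any short follow-up, whatever the milestone. It also counts patients who bled instead of bleeds, which is a separate matter and adds no weight here.

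**Conclusion.** The point holds as a conflict between planned dates and promised coverage. Followed as written, the milestone leaves 181 of 1,461 days (12.4%) of possible first administrations outside a population described as completely enumerated. A further 184 days (12.6%) cannot yield six months of data. The first part holds under the literal reading and under the last-first-dose reading. The second part holds only under the literal reading. If collection ran later than planned, the error is in the milestone row, and how far coverage falls short depends on the actual end date.

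For 95 registered subjects the number affected runs from zero to about 12 to 13 missed and 12 to 14 truncated. The upper figures rest on even uptake, and the spread within them on whether the 95 includes the missed users. The direction of any bias from truncation is downward for both the ABR and adverse event proportions. The documents do not allow its actual size to be known. That the promised coverage was in practice not achieved is an inference the documents cannot confirm.

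**What to change.** 1. Reconcile Protocol sections 4, 5, 7.2.3 and 7.5 by stating one cut-off for first administration and one date for the last record collected.
2. Restate the complete-enumeration claim for that window: for example, first infusion from 31 March 2014 to 30 September 2017 if the milestone stands as the cut-off. Moving the end date to 30 March 2018 alone is not enough, because late starters would still be truncated.
3. In the report, give the number of subjects with less than six months of data because of the cut-off, separately from those who stopped treatment.
4. In SAP 6.7, use actual observed time as the ABR denominator for all prophylaxis subjects. Doing so only for those cut by the calendar would mix two denominators and leave early discontinuers at 0.5 year.
5. Show the distribution of follow-up time beside the adverse event incidence proportions.

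The cost is a few sentences in the protocol, one changed denominator in the SAP, and a count and a follow-up summary in the report. First-administration and last-record dates are needed for each subject. The stated coverage becomes slightly less favourable.

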5. RATIONALE AND BACKGROUND

Xyntha Solofuse prefilled syringe was approved on March 31, 2014 in Korea. The Xyntha Solofuse prefilled syringe is administered by intravenous infusion after reconstitution of the freeze-dried powder with the diluent (0.9% Sodium Chloride). This drug consists of the identical ingredients with the previous Xyntha injection, and the drug and the diluent are supplied within the prefilled dual-chamber syringe. As required for all new drugs approved by the Ministry of Food and Drug Safety (MFDS), information on the safety and efficacy of the new drug should be provided based on the study conducted with at least 600 study subjects who are administered this drug in the setting of routine practice for 4 years from the approval date (March 31, 2014 - March 30, 2018). This non-interventional post-marketing surveillance (PMS) study is an obligation to the MFDS. However, it is expected that about 95 subjects who received this drug should be recruited and registered as study subjects. Considering the number of subjects who meet the analysis exclusion criteria, safety and efficacy information for at least 86 subjects will be collected for all subjects who received this drug during the study period. Background information on Xyntha Solofuse prefilled syringe can be obtained from the current version of the local product document, which is the single reference safety document (SRSD) for information relating to the Xyntha Solofuse prefilled syringe in this study.

6. STUDY OBJECTIVE

This study aims to observe the safety and efficacy of the Xyntha Solofuse prefilled syringe in the setting of routine practice. The primary objective is to detect medically significant events

(factor VIII inhibitor). The secondary objective is to observe the overall efficacy and safety of the Xyntha Solofuse prefilled syringe including serious adverse events.

7. STUDY METHODS

7.1. Study design

In this open-label, non-comparative, observational, non-interventional, retrospective and multi-center study, post-marketing surveillance data will be collected retrospectively for up to 6 months from the initial administration day of the Xyntha Solofuse prefilled syringe injected into patients who have been administered the Xyntha Solofuse prefilled syringe (as part of routine treatment at the Korean health care center which has certified investigators). If the study subject has not completed the 6-month treatment, relevant data should be collected based on the medical records within the 30 days after the last administration of the drug.

7.2. Setting

7.2.1. Inclusion criteria

To be eligible to enroll in this study, the study subjects will have to meet all the following inclusion criteria:

1. Hemophilia A (congenital factor VIII deficiency) patients who have been administered according to the indication of the product
 - 1) Control and prevention of bleeding episodes and for routine and surgical prophylaxis in patients with hemophilia A (congenital factor VIII deficiency)
 - 2) This drug does not contain von Willebrand factor and, therefore, is not indicated in von Willebrand's disease
2. Those who have been administered the Xyntha Solofuse prefilled syringe at least once

7.2.2. Exclusion criteria

Patients who satisfy the following criteria are not included in the study according to the local labeling:

1. Patients who have a history of hypersensitivity to the Xyntha Solofuse prefilled syringe or the ingredients of this drug.
2. Patients who have a history of hypersensitivity to hamster proteins.
3. Patients who have bleeding disorders other than hemophilia A.
4. Patients who have a history of FVIII inhibitors, or currently have or are suspected of having FVIII inhibitors. In case inhibitor titers quantified in Bethesda Units in the laboratory test results are within the normal laboratory range or at least 0.6 BU/mL. If

laboratory tests cannot be performed, the investigator will determine whether or not inhibitors exist based on the clinical assessment results that show a decrease in efficacy of the replacement of FVIII (e.g. bleeding at least once, if the replacement of anti-bleeding agents is needed to be administered, and if frequency or dosage of replacement FVIII therapy needs to be increased).

5. Use of immunomodulatory therapy. (e.g. intravenous injection of immunoglobulin, use of regular systemic corticosteroids, cyclosporine, and mediators of anti-TNF- α)

7.2.3. Study Period

As specified in the product approval issued by the Ministry of Food and Drug Safety, the study will be conducted for 4 years from the approval date of March 31, 2014 to March 30, 2018.

7.2.4. Administration and Dosage

This drug should be initiated under the supervision of a physician experienced in the treatment of hemophilia A.

This drug is appropriate for use in adults and children of all ages, including newborns.

Formula

$$\begin{array}{rclclclcl} \text{Required} & = & \text{body} & \times & \text{desired factor VIII rise} & \times & 0.5 \\ \text{units} & & \text{weight} & & \text{(IU/dL or normal \%)} & & \text{(IU/kg per IU/dL)} \\ & & \text{(kg)} & & & & \end{array}$$

Precise monitoring of the replacement therapy by means of plasma factor VIII activity assay should be considered, particularly for surgical intervention.

Dosing for Bleeding and Surgery

In the cases of the following hemorrhagic events, consideration should be given to maintaining the factor VIII activity at or above the plasma levels (in % of normal or in IU/dL) for the indicated period, as outline in the following table.

<Maintenance of Factor VIII Activity for Various Hemorrhagic Events>

Degree of Hemorrhage/ Type of surgical procedure	Factor VIII Level Required (% or IU/dl)	Frequency of Doses (hours) /Duration of Therapy (days)
Bleeding Early hemathrosis, minor muscle or oral bleeds	20-40	Repeat every 12 to 24 hours as necessary until resolved. At least 1 day, depending upon the severity of the bleeding episode.
Bleeding into muscles. Bleeding into the oral cavity. Mild head trauma.	30-60	Repeat infusion every 12 to 24 hours for 3-4 days or until adequate local hemostasis is achieved.
Gastrointestinal bleeding. Intracranial, intra-abdominal or intrathoracic bleeding. Fractures.	60-100	Repeat infusion every 8 to 24 hours until bleeding is resolved.
Surgery Minor operation (including tooth extraction)	30-60	Repeat infusion every 12 to 24 hours for 3-4 days or until adequate local hemostasis is achieved. For tooth extraction, a single infusion plus oral antifibrionlytic therapy within 1 hour may be sufficient.
Major operation	60-100	Repeat infusion every 8 to 24 hours until threat is resolved, or in the case of surgery, until adequate local hemostasis and wound healing are achieved. Then continue therapy for at least another 7 days to maintain the factor VIII activity at 30 to 60% (IU/dl)

Dosage for Prophylaxis

This drug has been administrated prophylactically in a pivotal clinical trial in adolescent and adult previously treated patients at a dose of 30 ± 5 IU/kg given 3 times weekly.

Administration

This drug is administered by intravenous (IV) infusion after reconstitution of the freeze-dried powder with the diluent (0.9% Sodium Chloride). Both the Xyntha powder and the diluent are supplied within the prefilled dual-chamber syringe.

Patients administered Xyntha Solofuse prefilled syringe 250 IU, 500 IU, 1000 IU, 2000 IU, or 3000 IU at least once in the routine practice will be observed. All the enrolled subjects

should meet the general prescription criteria of Xyntha Solofuse prefilled syringe according to the local product document, and should be included in this study based on the judgment of the investigator.

7.2.5. Study Procedures

The investigator collects data on the Xyntha Solofuse prefilled syringe retrospectively by recording the data in the case report form from the initial administration day up to 6 months from patients who have been administered the Xyntha Solofuse prefilled syringe at least once or are scheduled to be administered the Xyntha Solofuse prefilled syringe.

This study does not have scheduled visit dates because it is not an interventional study. Safety data will be collected at each visit. If a study subject experiences bleeding episodes during the up to 6-month observation period, the clinical response to the treatment required for each bleeding episode will be evaluated.

